3.3. Approach

3.3.1. Research Design. This research design is illustrated in Fig 5. Aim 1 will use a cross-sectional design to determine baseline relationships between AGE level, intrinsic foot muscle volume, ankle joint mobility, MTPJ movement patterns and MTPJ extension alignment at baseline. Aim 2 is a clinical study with the foot specific intervention focused on improving foot and ankle strength, mobility, and function. The control group will receive a meaningful, comparable, but distinct intervention targeted at improving shoulder mobility, a common limitation in those with DMPN. All participants will repeat testing at 6 months, 1.5 years, and 3 years. Aim 3 will determine the key variables that predict progression of MTPJ extension deformity at 1.5 and 3 years. Intervention status will be entered as a potential predictor variable to examine the ability of a foot specific intervention to impact deformity progression.

Sixty-two participants with DMPN (defined below) and a wide range of MTPJ extension angle will be recruited and followed for 3 years. We will recruit a wide range of MTPJ extension angles to have broad variance in the magnitude and presentation of this deformity so we can understand better the primary factors with which it is associated. We will not break participants into groups based on amount/severity of MTPJ hyperextension allowing us to maintain the continuous nature of important predictors and dependent variables, and hence, increase power of our repeated measures research design.^{55, 56} Only participants with DMPN will

Figure 5: Research Design

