be recruited (vs. otherwise healthy people with MTPJ deformity) so we can focus on the muscle and limited joint mobility problems unique to DMPN. Measures will be taken at baseline, as described below in Table 1, and then all participants will be randomized into a foot specific or a shoulder specific intervention group. Participants will receive 6 intervention visits and a home program. Physical therapist directed interventions will occur during the first 4 months of study participation (3 visits in the first month, and then 1 per month for 3 months). Participants will be instructed, and encouraged by phone call follow up, to continue the home program for the duration of study enrollment. The research coordinator will call participants every 3 months to determine any change in medical status (i.e., skin breakdown, medical emergency), assess adherence with the home program and to keep them “connected” to the study. Participant testing will be repeated at 6 months, 1.5 years, and 3.0 years so that impact of treatment and predictors of change in deformity can be examined. Although we consider this clinical study preliminary, testers will be blinded to group assignment, treatments will take place in a different location than the assessments, and CONSORT guidelines will be followed.

Sample size determination.

Aim 1: A power analysis was conducted based on Hsieh et al's⁵⁷ sample size calculation for logistic and linear regression. 62 participants with DMPN are needed to detect a significant correlation of .44 between the predictor (intrinsic foot muscle volume) and the dependent variable (baseline MTPJ alignment) after adjusting for the other variables (AGE level, maximum ankle dorsiflexion, and maximum MTP extension during ankle dorsiflexion tasks), assuming all the predictors account for 37% of baseline MTPJ alignment. We are confident we will achieve these values for aim 1 since our preliminary data showed a higher correlation ($r=0.60$).

Aim 2: The power analysis for the pilot clinical study is based on a two-sample t-test. We anticipate an effect size of mean ankle joint dorsiflexion range of motion at 6 months, between the foot and shoulder specific intervention groups, of $4 \pm 5^\circ$.⁴⁶ A sample of 52 (26 in each group) will be able to detect this effect size. Our targeted sample size 62 is conservative for this aim considering very low attrition rate at 6 month.

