Aim 3: There is little existing evidence documenting the progression of diabetic foot deformity and we acknowledge that our work proposed in aim 3 is novel and exploratory. Aim 3 Ho3 is powered based on anticipated mean progression of MTPJ alignment 4° every 1.5 years after baseline in 50% people with DMPN assuming a standard deviation of 7.6° with a two-sided paired t-test. We assumed a much more conservative correlation of 0.6 between MTPJ alignment at baseline and 1.5 years later. Our preliminary data documented a progression in midfoot angle deterioration (Meary's angle) that worsened from -15.1 (14.3°) to -22.8 (14.2°) over 2 years in a group of subjects with a history of midfoot deformity, a correlation between measurement time points of 0.81.⁵⁸ Assuming a 20% attrition of the recruited sample, results in a required sample size of 62.

3.3.2. Subject recruitment will occur primarily from the Recruitment Enhancement Core of the Institute of Clinical And Translational Sciences here in the medical center. Several data bases are available to help recruit (e.g., Research Participant Registry through Volunteers for Health, and patient databases of the Applied Biomechanics and Human Biodynamics Laboratories). These resources have sufficient numbers of potential participants to help us achieve our goal. Potential participants will be mailed the consent prior to their first visit to allow them to carefully review the information and formulate questions regarding the study requirements. The requirements, risks and benefits of participation will be explained and all questions the potential participant may have will be answered. If willing to enroll in the study, written informed consent will be obtained. The potential participants will be screened and included if they meet the following inclusion and exclusion criteria:

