Inclusion criteria: Subjects must have Type 2 DM and diabetic PN. The presence of PN will be determined by 1) inability to sense a 5.07 Semmes-Weinstein monofilament on at least one location on the plantar foot, 2) a vibration perception threshold on the plantar great toe greater than 25 V as measured by a biothesiometer, AND 3) an examination score on the Michigan Neuropathy Screening Instrument >2 . As part of the screening process and to ensure a wide range of MTPJ deformity, we will estimate magnitude of MTPJ deformity using a goniometer and our previously published methods⁵⁹ to recruit 1/3 of subjects in each of the following 3 categories of MTPJ severity; $<30^\circ$, $30-50^\circ$, and $>50^\circ$.^{13, 60}

Exclusion criteria: PN with causal factor other than DM (i.e., alcoholic, chemo toxic, lumbar radiculopathy); dialysis; severe arterial disease (ABI < 0.9 or > 1.3)¹; rigid MTPJ deformity; metal implants or pace makers which would interfere with MRI data collection; unable to physically complete testing for the study; lower extremity amputations including multiple toes; acute shoulder pain or disability that would prevent participation in shoulder specific intervention (i.e. severe shoulder pain $>6/10$, rotator cuff tear, upper extremity surgery, thoracic outlet syndrome); pregnant; weight greater than 180 kg (MRI table limitations); presence of a neuropathic ulcer; or age greater than 75 (to minimize extreme age related changes on muscle or joint).

The age exclusion will not be applied for the walking study. Also, MRI compatibility characteristics (e.g., metal implants or pacemakers, pregnant, weight) and shoulder problems will not be applied for the walking study. For the participants in the walking study, people who have neurological disorders (e.g., Parkinson's disease, stroke, multiple sclerosis) that may change walking behavior and use the assistive device when walking will be excluded.

	Time (min)	Baseline (T1)		1- 15 Weeks		6 Month (T2)		7-17 Months		Year 1.5 (T3)		19-35 Months		Year 3 (T4)	
		Visit 1	Visit 2	Visit 1	Visit 2	Visit 1	Visit 2	Visit 1	Visit 2	Visit 1	Visit 2	Visit 1	Visit 2	Visit 1	Visit 2
Informed Consent	15	✓													
Clinical Intake Data	30	✓				✓				✓				✓	
Instrumented Measures															
Skin Fluorescence	10	✓												✓	
Magnetic Resonance	30		✓				✓								✓
Computed Tomography	15		✓				✓				✓				✓
Kinematic Assessment	90	✓				✓				✓				✓	
Clinical Measures															

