3.3.4.2. Spiral CT Scanning for MTPJ Deformity and Joint Positions: The purposes of using spiral CT scans for this project are to measure: 1) MTPJ alignment over the 3 year follow up period, 2) measure precisely maximum ankle joint dorsiflexion, and 3) maximum MTPJ active flexion in resting position. CT scans and measurements will be taken in 3 positions. At Visit 4 an additional CT scan will be taken of the foot not followed as part of the study for a comparison.

- 1) Resting position - the calf and foot are placed on a positioning device to standardize ankle position in resting position of 30° plantar flexion (approximate mid position of physiological ankle range of motion from 10° dorsiflexion to 50° plantar flexion, see Fig. 7).^{13, 59} The measure of MTPJ angle in resting position will serve as our primary outcome measure defining the amount of MTPJ hyperextension. MTPJ alignment will be defined as the angle between the phalanx and the extension of the bisector of the metatarsal. A larger angle will indicate less deformity.^{13, 67} (Aims 1-3, Fig. 8).
- 2) Maximum active ankle dorsiflexion - The study participant will be instructed to maximally dorsiflex their ankle joint. Maximum active ankle dorsiflexion and concurrent MTPJ angle will provide the measure of ankle mobility for Aims 1 &2 and an indicator of MTPJ hyperextension movement pattern for Aims 1-3. (Fig. 8b)
- 3) Maximum active MTPJ flexion – The study participant will be instructed to maximally flex their MTPJ with their foot supported in the positioning device. Maximum active MTPJ flexion is an exploratory outcome measure that should improve with the foot specific intervention through increasing MTPJ joint mobility and intrinsic muscle strength. (Fig. 8c)

[figure not shown]

Figure 8. CT positions for measuring MTPJ and ankle angles. MTPJ alignment is the angle between the phalanx and the extension of the bisector of the metatarsal. A larger MTPJ angle indicates less deformity.

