3.3.5 Intervention. Participants will be randomly assigned to receive either a foot specific (experimental) or shoulder specific (control) intervention. The rationale for the **foot specific (experimental) intervention** is described in section 3.1.5 and will consist of a progressive exercise program, outlined in Appendix A. The foot specific program is an adaptation of the exercise program used in our previous randomized controlled trial to increase walking tolerance in people with DMPN and which was found to improve not only walking tolerance, but also ankle dorsiflexion range of motion and Foot and Ankle Ability Measure scores.⁴⁶ Other research has shown the ability to improve foot function outcomes in the elderly and others,^{47, 48} but to our knowledge, there is no other evidence besides our own randomized controlled trial that has investigated whether an exercise and movement program can improve foot-related outcomes in people with DMPN. Unlike our previous randomized controlled trial that aimed primarily to increase weight-bearing activity, this foot specific intervention will consist of a carefully prescribed progressive home program that will include passive stretching of the ankle and MTPJs, strengthening of the foot intrinsic and ankle plantarflexor muscles, and movement pattern training to reduce toe extension associated with active dorsiflexion movements. (Appendix A) The overall goal is to improve specific muscle strength, joint range of motion and movement patterns to minimize MTPJ deformity.

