Aim 1: A multiple linear regression analysis will be used to test Aim 1. The primary dependent variable for Aim 1 will be baseline MTPJ alignment. The independent variables (predictors) for Aim 1 will be AGE level, intrinsic foot muscle volume, maximum ankle dorsiflexion, and MTPJ extension excursion during sit to stand. A Pearson correlation matrix will be obtained on all variables to understand better inter correlations. Adjusted R square from the multiple linear regression model will be obtained.

Aim 2: A repeated measures ANOVA analysis will be used to estimate the effect of the intervention by determining the between group changes over time in the primary outcome measures MTPJ extension alignment and the secondary outcome measures of intrinsic muscle volume, ankle joint dorsiflexion range of motion, MTPJ extension excursion during sit-to/from-stand and Foot and Ankle Ability Measure. Contrasts will be used to determine mean differences of interest.

Aim 3 Ho3: MTPJ deformity progression will be calculated as progression every 1.5 years (MTPJ deformity at baseline – MTPJ deformity at 1.5 years and MTPJ deformity at 1.5 years – MTPJ deformity at 3 years). Means and standard deviations for these differences will be obtained and paired t-tests will be performed to test for significant progression every 1.5 years. The proportion of individuals with DMPN and MTPJ deformity progression at 4 degrees or more within 1.5 years will be calculated with 95% confidence interval.

Aim 3 Ho4: MTPJ deformity progression will be assessed as progression at 1.5 and 3 years (MTPJ deformity at baseline – MTPJ deformity at 1.5 years and MTPJ deformity at baseline – MTPJ deformity at 3 years). Analysis of covariance model will be fitted to these two progression variables with intervention status as the major predictor adjusting for baseline measures of AGE level, intrinsic foot muscle volume, MTPJ extension excursion during sit to stand.

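### The Ho4 model for change in MTPJ alignment leaves out baseline MTPJ angle, so a chance baseline difference between arms is only partly corrected and some precision is lost

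*Combined protocol and SAP*

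**What the plan says.** **Allocation.** Section 3.3.1 has baseline testing first, and then "all participants will be randomized into a foot specific or a shoulder specific intervention group". Section 3.3.5 repeats this: "Participants will be randomly assigned to receive either a foot specific (experimental) or shoulder specific (control) intervention". The human-subjects section says the same. None of these places gives a stratification factor, block size or method of generating the sequence. The plan does commit to CONSORT.

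**Sample.** Section 3.3.2 uses a goniometer at screening "to recruit 1/3 of subjects in each of the following 3 categories of MTPJ severity": below 30, 30 to 50 and above 50 degrees. Section 3.3.1 adds "We will not break participants into groups based on amount/severity of MTPJ hyperextension", giving as its reason that predictors and outcomes should stay continuous.

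**Outcome.** Section 3.3.4.2, on the CT scans: "The measure of MTPJ angle in resting position will serve as our primary outcome measure defining the amount of MTPJ hyperextension". Table 1 schedules CT at baseline, 6 months, 1.5 years and 3 years.

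**Analysis (section 3.3.6).** For Ho4, "MTPJ deformity progression will be assessed as progression at 1.5 and 3 years", each taken as baseline minus follow-up. The ANCOVA has intervention status as its main predictor, "adjusting for baseline measures of AGE level, intrinsic foot muscle volume, MTPJ extension excursion during sit to stand". Baseline MTPJ angle is not listed. Aim 2 uses repeated measures ANOVA on between-group changes over time and names no baseline covariate.

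**The concern.** Recruitment deliberately widens the spread of the primary outcome at baseline, and only 62 people are then divided between two arms. With 21, 21 and 20 people in the three categories and an unstratified 31:31 split, some category differs between arms by 5 or more people in 48% of allocations (by simulation).

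Subtracting baseline does not fully remove such a difference. When baseline and follow-up correlate imperfectly, people with extreme baseline angles tend to move back towards the mean, so change is itself correlated with baseline. An arm that starts with more extreme angles will then show a different average change without any treatment effect. Ho4 is where the plan asks whether the intervention slows progression, and the one variable that would remove this effect is already collected but not in the model.

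**Working it through.** **Inputs from the documents.** Total 62, and an implied 1:1 allocation (Aim 2 has 26 per group), so 31 per arm. Aim 3 planning values: SD 7.6 degrees, correlation r = 0.6 and progression of 4 degrees in 50% of people. Preliminary midfoot-angle correlation: 0.81. Pilot correlation of muscle volume with MTPJ angle: 0.60 (section 3.3.4.3).

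**Assumptions.** 80% power, since none is stated. The SD of baseline MTPJ angle in the enrolled sample is not given, so a range is used. Angles spread evenly within the screening bands, with outer limits of 20 to 60 or 10 to 70 degrees, give SDs of 12.9 and 17.3.

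**Step 1: the plan's own figure.** SD of change = 7.6 × √(2 × (1 − 0.6)) = 6.80. A paired t-test for 4 degrees at 80% power needs 25 people. Then 25 / 0.5 / 0.8 = 62.5, which agrees with the plan: "Assuming a 20% attrition of the recruited sample, results in a required sample size of 62". So 7.6, 0.6 and 6.80 belong together.

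**Step 2: chance of a 4-degree baseline gap without stratification.** SE of the gap = SD × √(2/31).

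| Baseline SD | SE of gap | P(gap of 4 degrees or more) |
|---|---|---|
| 7.6 (plan) | 1.93 | 3.8% |
| 12.9 (assumed) | 3.28 | 22% |
| 17.3 (assumed) | 4.39 | 36% |

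The recruitment quota makes 7.6 look low on the goniometer scale. Even with thirds placed exactly at 30, 40 and 50, the SD is √((100 + 0 + 100)/3) = 8.2, which gives about 5%.

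**Step 3: how much of a gap reaches the Ho4 contrast.** With equal SDs at both times, a change score carries over (1 − r) of each degree. If muscle volume is in the model, correlates 0.60 with baseline angle and is related to change only through it, this is multiplied by 1 − 0.60² = 0.64.

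- r = 0.6: 0.40 for the change score alone. With muscle volume, 0.40 × 0.64 = 0.26 (0.25 to 0.27 in simulation; 0.27 is used below).
- r = 0.81: 0.19 alone; 0.19 × 0.64 = 0.12 with muscle volume.
- Baseline SD 12.9 or 17.3 with the plan's SD of change kept at 6.80: r = 1 − 6.80²/(2 × SD²) = 0.86 or 0.92, so carry-over is 0.14 or 0.08 before any covariate.
- Baseline angle in the model: about 0 in every simulated setting.

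**Step 4: shift in the arm contrast from a 4-degree gap.**

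| Setting | Chance of gap | Carry-over per degree | Shift (degrees) |
|---|---|---|---|
| SD 7.6, r = 0.6 | 3.8% | 0.27 to 0.40 | 1.1 to 1.6 |
| SD 7.6, r = 0.81 | 3.8% | 0.12 to 0.19 | 0.5 to 0.8 |
| SD 12.9, SD of change 6.80 | 22% | 0.14 | 0.6 |
| SD 17.3, SD of change 6.80 | 36% | 0.08 | 0.3 |

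**Step 5: precision.** In simulation at r = 0.6, adding baseline angle to a model with arm and muscle volume lowered the SE of the arm effect from 1.677 to 1.558 (7.1%) at SD 7.6, and from 3.299 to 3.096 (6.2%) at SD 15. At r = 0.81 the gains were 2.5% and 2.1%. AGE level and excursion were not simulated. Excursion (pilot r = 0.48 with alignment) may absorb a little more.

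**The case against.** The strongest reply is that most of the protection is already there. The Ho4 outcome subtracts baseline, which removes 60% of a gap at r = 0.6 and about 80% at r = 0.81. Muscle volume removes more. Aim 2 likewise compares changes, not raw follow-up means. Randomisation makes the estimate unbiased over allocations, and its standard error already includes this variation. The plan calls the clinical study preliminary and Aim 3 exploratory. All of this stands, and it limits the size of the point.

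It does not remove the point. A remainder carries over in every setting above. The help from muscle volume is not guaranteed either, because section 3.3.6 allows predictors to be dropped for collinearity or examined singly or in small subsets. The statement about not grouping by severity is no defence: it concerns keeping variables continuous, and a continuous baseline covariate respects it.

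A reader might infer three stronger things that the documents do not support:

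- **That allocation is simple and disregards severity.** The documents are silent on the method. The supportable statement is that no stratification is stated.
- **That a 22% to 36% chance of a 4-degree gap goes with a 1.6-degree shift, 40% of the planned progression.** This pairs an assumed SD of 13 to 17 with the r = 0.6 that the plan pairs with 7.6. It implies an SD of change of 12.9 × √0.8 = 11.5 to 17.3 × √0.8 = 15.5 degrees, about twice the plan's 6.80.
- **That stratifying would cut the chance of such a gap to 1% or less.** That figure treats the screening goniometer estimate as if it were the CT angle, and assumes even spread within bands whose outer limits are not given.

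**Conclusion.** The point holds as an avoidable omission from the Ho4 model. If the arms happened to differ by 4 degrees at baseline, the contrast in change would move by about 0.3 to 1.6 degrees, or 8% to 40% of the 4-degree progression used for planning. The top of that range belongs with the plan's SD of 7.6, where such a gap has about a 4% chance. At assumed SDs of 13 to 17 the gap is likelier (22% to 36%), but with the plan's SD of change the shift is only 0.3 to 0.6 degrees.

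It would be wrong to call this systematic bias, or to say that imbalance goes uncorrected. It is a chance shift in a single trial, together with a standard error larger than necessary: by about 6% to 7% at r = 0.6, and less at higher correlations. The figures assume equal SDs at both times and 31 per arm, and they depend on a baseline SD that the documents do not report.

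**What to change.** 1. **Ho4:** add the continuous baseline CT resting MTPJ angle as a prespecified covariate in both ANCOVAs (1.5 and 3 years), and exempt it from the provision for dropping predictors. This takes the carry-over to about zero whether or not allocation was stratified.
2. **Aim 2:** model the follow-up MTPJ angles with baseline as a covariate, instead of including baseline as one of the repeated responses.
3. **Reporting:** state how the allocation sequence was generated and whether it was stratified or blocked.
4. **Optional, only if enrolment is still open:** stratify the randomisation in blocks by the three screening categories. With about 20 people per category, the price is a few incomplete blocks. This is secondary, because the covariate alone removes the carry-over.

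Items 1 and 2 need no new data and cost one degree of freedom per model. One consequence should be noted in the plan: the Ho4 coefficients for AGE level, muscle volume and excursion would then be read as conditional on baseline angle. If those are wanted without that condition, the currently planned model can be reported alongside as a secondary analysis.

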All statistical tests will be two-sided with a significance level of 0.05 and performed with SAS 9.4. Careful attention will be paid to ensuring that data satisfy assumptions required of a particular analytic strategy. Thus, paired t-tests will only be accepted as valid if normality assumptions are satisfied. Similarly, we will evaluate regression residuals before we reach conclusions based on linear regression analysis. When required assumptions are violated, we will explore the use of data transformations and potentially, perform some analyses using non-parametric or semi-parametric methods based on the rank of some variables. In the event of multicollinearity with numerous predictors in regression models, highly redundant variables will be eliminated from the analyses, or where possible, composite variables will be formed to capitalize on the higher reliability of combined measures. Sample size limitations and potential multicollinearity may preclude the examination of all predictors in one analysis. To avoid this problem, we will examine the impact of predictors individually or in small, conceptually sensible, subsets.

3.3.7. Proposed Timeline and Plans for Future Studies.

We propose to complete the aims of this project in 5 years with the following milestones:

9/1/2015 – start date; Year 1: Methods and personnel are ready to begin testing immediately. Based on current recruitment methods, we are confident we can recruit and test 4 subjects per month. Therefore, we plan to conduct all baseline testing in the first 16 months of the study; 48 in year 1 and 14 in year 2. Data processing and entry into databases will occur on an on-going basis. Intervention will be initiated immediately after baseline testing has been completed

Year 2: Participant recruitment, baseline testing, intervention and 6 month follow up testing will be completed in year 2. Data analysis for baseline measures and the manuscript related to Aim 1 will be completed by the end of year 2. 1.5 year re-testing will begin on 24 subjects. Data analysis for Aim 2, 6 month data will be analyzed and the related manuscript prepared for publication.

Year 3: Complete 1.5 year re-testing on remaining 38 participants for total of 62 participants. Analyze and summarize all data.

Year 4: Complete 3 year retesting on 48 participants.

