Participants will be randomized into a foot specific or a shoulder specific intervention group. Participants will receive 8 intervention visits and a home program. Physical therapist directed interventions will occur during the first 5 months of study participation (3 visits in the first month, 2 visits in the second month and then 1 per month for 3 months), with a home program to be completed independently, 5 times/week-estimated to take 30 minutes to complete. Participants will be instructed, and encouraged by phone call follow up, to continue an abbreviated home program, 3 times/week-estimated to take 15 minutes to complete, for the duration of study enrollment. The research coordinator will call participants every 3 months to determine any change in medical status (i.e., skin breakdown, medical emergency), assess adherence with the home program and to keep them “connected” to the study. Participant testing will be repeated at 6 months, 1.5 years, and 3.0 years so that impact of treatment and predictors of change in deformity can be examined. Although we consider this clinical study preliminary, testers will be blinded to group assignment, treatments will take place in a different location than the assessments, and CONSORT guidelines will be followed.

Sample size.

Aim 1: A power analysis was conducted based on Hsieh et al's⁵³ sample size calculation for logistic and linear regression. 62 participants with DMPN are needed to detect a significant correlation of .44 between the

predictor (intrinsic foot muscle volume) and the dependent variable (baseline MTPJ alignment) after adjusting for the other variables (AGE level, maximum ankle dorsiflexion, and maximum MTP extension during ankle dorsiflexion tasks), assuming all the predictors account for 37% of baseline MTPJ alignment. We are confident we will achieve these values for aim 1 since our preliminary data showed a higher correlation ($r=0.60$).

Aim 2: The power analysis for the pilot clinical study is based on a two-sample t-test. We anticipate an effect size of mean ankle joint dorsiflexion range of motion at 6 months, between the foot and shoulder specific intervention groups, of $4 \pm 5^\circ$.⁴⁶ A sample of 52 (26 in each group) will be able to detect this effect size. Our targeted sample size 62 is conservative for this aim considering very low attrition rate at 6 month.

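### Aim 2 measures the intervention effect as between-group change with no baseline covariate, a valid analysis that gives up precision the trial could have at almost no cost

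*Combined protocol and SAP*

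**What the plan says.** Section 3.3.6, Aim 2, uses a repeated measures ANOVA to "estimate the effect of the intervention by determining the between group changes over time". The primary outcome is MTPJ alignment. The secondary outcomes are intrinsic muscle volume, ankle dorsiflexion range of motion, MTPJ excursion during sit-to/from-stand, and the Foot and Ankle Ability Measure. The text adds only that "Contrasts will be used to determine mean differences of interest". It lists no covariate and does not say how the baseline value enters. In the same section, Aim 1 lists its predictors by name, and Aim 3 Ho4 is an analysis of covariance with named adjustment variables.

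Section 3.3.1 places baseline measurement before randomisation. Table 1 schedules CT, MRI, kinematics, questionnaires and joint mobility at both baseline and 6 months, so every Aim 2 outcome has its own baseline value.

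The Aim 2 sample size, given in 3.3.1 and repeated under Protection of Human Subjects, rests on a different test: "The power analysis for the pilot clinical study is based on a two-sample t-test". The paragraph continues: "We anticipate an effect size of mean ankle joint dorsiflexion range of motion at 6 months", with a between-group figure of 4 ± 5°. It concludes: "A sample of 52 (26 in each group) will be able to detect this effect size". It states no power and no correlation between baseline and 6 months, and it does not say whether 5° is the SD at 6 months or the SD of change. Recruitment is set at 62.

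**The concern.** If baseline is an outcome visit, a 6-month contrast subtracts each participant's full baseline value. That removes stable differences between people but adds the noise of the baseline measurement. Baseline as a covariate subtracts only the part of the baseline value that predicts follow-up. In a randomised comparison both approaches target the same difference, and with equal variances the covariate version is never the noisier one. Raw changes also over-correct chance baseline differences between arms, which are likely with 26 to 31 per arm.

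What is at stake is the precision of the intervention effect on every Aim 2 outcome, including those with no power calculation. There is a second, smaller matter: the test used for sizing is not the planned analysis, and without knowing what 5° is, a reader cannot tell how the two relate.

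**Working it through.** **Inputs from the plan.** Difference 4°, SD 5°, 26 per arm (52 in total) and a target of 62 (31 per arm if allocation is equal), from the sample size text in 3.3.1. Two-sided 0.05, from 3.3.6. 

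**Assumptions.** The correlation rho between baseline and 6-month dorsiflexion is not given, so it is varied. The nearest figures, in the Aim 3 sample size text, are 0.6 (assumed for MTPJ alignment over 1.5 years) and 0.81 (Meary's angle over 2 years). Variances at the two visits are taken as equal.

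**Step 1: reproduce the 52.** The noncentrality is 4 / (5 × √(2/26)) = 2.88 on 50 degrees of freedom, which gives power of 80.7%. The smallest n per arm by noncentral t is 26 for 80%, 30 for 85% and 34 for 90%. The 52 therefore reproduces at 80%, a level that is inferred because the plan does not state it. With 31 per arm the same t-test has 87.3%.

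**Step 2: error SD under each analysis, if 5° is the SD at 6 months.**
- 6-month t-test: 5
- change contrast: 5 × √(2(1−rho))
- baseline-adjusted: 5 × √(1−rho²), with one error degree of freedom fewer

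The variance ratio, adjusted to change, is (1−rho²) / (2(1−rho)) = (1+rho)/2. This is below 1 for every rho below 1. At rho 0.6 it is 0.80, so the change contrast carries 1/0.80 = 1.25 times the variance.

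**Step 3: power for 4°, if 5° is the SD at 6 months.**

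| rho | SD change / adjusted | 26 per arm: change → adjusted | 31 per arm: change → adjusted |
|---|---|---|---|
| 0.3 | 5.92 / 4.77 | 66.7% → 84.2% | 74.5% → 90.1% |
| 0.4 | 5.48 / 4.58 | 73.3% → 87.0% | 80.8% → 92.2% |
| 0.5 | 5.00 / 4.33 | 80.7% → 90.4% | 87.3% → 94.7% |
| 0.6 | 4.47 / 4.00 | 88.5% → 94.2% | 93.4% → 97.2% |
| 0.8 | 3.16 / 3.00 | 99.4% → 99.7% | 99.8% → 99.9% |

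The change contrast falls below 80% power only when rho is under about 0.49 with 52 participants, or under about 0.39 with 62. At rho 0 the adjusted analysis with 26 per arm still has 80.7%, so adjustment costs nothing material even if baseline is uninformative.

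**Step 4: power if 5° is already the SD of change.** The change contrast then has the sized 80.7% whatever rho is. The adjusted SD is 5 × √((1+rho)/2). With 26 per arm this is 4.33 at rho 0.5 (90.4%), 4.47 at rho 0.6 (88.5%) and 4.74 at rho 0.8 (84.6%). The gain at rho 0.8 is thus under 4 points on either reading of 5°.

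**The case against.** A reader might infer that the 52 participants fail to deliver the power they were sized for. The documents do not support that, for four reasons.

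- It needs two unstated conditions together: 5° must be the SD at 6 months, and rho must be below about 0.5. If 5° is the SD of change there is no shortfall. Section 3.1.5 reports the earlier exercise trial's dorsiflexion result as an increase of 4.1°, and the sizing paragraph cites the same trial, so the change reading is at least as plausible.
- The plan's only serial correlations, 0.6 and 0.81, lie above 0.5, although they belong to other measures over longer intervals. At those values the change contrast has more power than the sizing t-test: 88.5% and 99.6% with 26 per arm.
- 52 is the minimum. The target is 62, with very low attrition expected at 6 months.
- The rho threshold belongs to a 6-month-minus-baseline contrast, which the plan does not name. In a simulation with four equally correlated visits and a 4° effect at every follow-up, 26 per arm and rho 0.5, the overall group-by-time test had 85.0% power.

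All of this stands, and so does the remark that the text never says outright that baseline is an outcome visit; that is an inference from the wording and from the absence of covariates. A group-by-time comparison in a randomised trial is also a legitimate analysis, the clinical study is described as preliminary, and dorsiflexion is a secondary outcome. None of this removes the efficiency argument, because the ratio (1+rho)/2 depends on neither the reading of 5° nor any threshold for rho.

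**Conclusion.** The point holds as one of efficiency and specification. As written, Aim 2 most naturally compares raw changes, and adjusting for each outcome's own baseline would be more precise at any correlation below 1.

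At rho 0.5 to 0.6, with 5° as the SD at 6 months, the gain in power for dorsiflexion is about 10 to 6 points with 26 per arm and about 7 to 4 points with 31. With 5° as the SD of change it is about 10 to 8 points with 26 per arm. It becomes small as rho approaches 0.8. These figures rest on equal variances across visits and on an assumed rho; the variance ratio carries over to the other Aim 2 outcomes, the power figures do not.

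It does not follow that the test is invalid or the trial too small. A shortfall against the sizing calculation is possible only if 5° is the SD at 6 months and rho is below about 0.5 with 52 participants, or below about 0.39 with 62.

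**What to change.** In 3.3.6, Aim 2, prespecify for each outcome a repeated measures model with the follow-up visits as outcomes (6 months, 1.5 years and 3 years, where that outcome is measured). The predictors are arm, visit, arm-by-visit, the outcome's own baseline value and baseline-by-visit. Report the adjusted arm difference at each visit. A longitudinal model that keeps baseline as an outcome but constrains the arm means to be equal there would serve equally well.

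In both copies of the Aim 2 sample size paragraph (3.3.1 and Protection of Human Subjects), state whether 5° is the SD at 6 months or the SD of change, and give the power and the baseline to 6-month correlation assumed.

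The cost is a sentence or two of wording and a few model degrees of freedom: with three follow-up visits, one for baseline plus two for baseline-by-visit. No new data or participants are needed.
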